## 1. Background and rationale

### 1.1 Acute Lymphoblastic Leukemia

Acute leukemias are the most common malignancies in children, accounting for 32% of all cancers in children <15 years of age. Acute lymphoblastic leukemia (ALL) accounts for 80% of childhood leukemia. The annual incidence of ALL is approximately 5 per 100,000 population, peaking at 9 per 100,000 among children 1 to 4 years of age.[1] With current chemotherapy protocols the prognosis is excellent with 5-year survival of over 85%.

#### 1.1.1 Chemotherapy regimens and their immunosuppressive effects

At diagnosis, children are stratified as standard, high or very high risk, depending on clinical and genetic features. The clinical features that predict high risk ALL are: male sex, age <1 year or ≥10 years at diagnosis, presenting peripheral white blood cell (WBC) count ≥50 x10^9/l.

Treatment consists of multiple phases of multi-drug systemic and intrathecal chemotherapy: induction, consolidation, interim maintenance, delayed intensification and maintenance therapy. Total treatment course is approximately 2 years for girls and 3 years for boys. Most pediatric oncology centres in Canada use the treatment protocols developed by the Children's Oncology Group (COG). Three centres use the protocols developed by the Dana-Farber Cancer Institute (DFCI) ALL Consortium.[2] Examples of standard and high risk COG and DFCI ALL protocols are shown in Tables 1 and 2.

**Table 1. COG ALL chemotherapy protocol (AALL0932)**

	Induction	Consolidation	Interim Maintenance I/II	Delayed Intensification	Maintenance
SR-ALL	5 weeks	4 weeks	8 weeks	8 weeks	to complete 2-3 years total therapy
	Vincristine, Dexamethasone, Pegaspargase; IT Methotrexate & Cytarabine	Vincristine, Mercaptopurine; IT Methotrexate	Vincristine, Methotrexate; IT Methotrexate	Dexamethasone, Vincristine, Doxorubicin, Pegaspargase, Cyclophosphamide, Thioguanine, Cytarabine; IT Methotrexate	Vincristine, Dexamethasone, Mercaptopurine, Methotrexate; IT methotrexate
HR-ALL	5 weeks	8 weeks	9 weeks	8 weeks	to complete 2-3 years total therapy
	As above + Daunorubicin	As above + Cyclophosphamide, Cytarabine, Pegaspargase	As above with high dose Methotrexate + Leucovorin	As above	As above with Prednisone instead of Dexamethasone

SR, standard risk; HR, high risk; IT, intrathecal

Multi-drug chemotherapy leads to profound bone marrow suppression as well as specific impairment of innate, cell-mediated and humoral immune responses. Consequently, infection is the most common cause of treatment-related mortality, with a cumulative risk of 3%. [3-5]

**Table 2. DFCI ALL treatment protocol 95-01.[2]**

	Induction	CNS therapy	Intensification	Continuation
SR-ALL	4 weeks	3 weeks	30 weeks	Until 24 months continuous remission
	Vincristine, Prednisone, Doxorubicin Asparaginase; IT Cytarabine, IT Methotrexate, IT Hydrocortisone	IT Methotrexate & Cytarabine +/- cranial radiation	Vincristine, Prednisome Methotrexate 6-Mercaptopurine Asparaginase	Vincristine, Prednisome Methotrexate 6-Mercaptopurine
HR-ALL	4 weeks	3 weeks	30 weeks	Until 24 months continuous remission
	As above +/- Dexrazoxane	As above + cranial radiation for all	As above + Doxorubicin +/- Dexrazoxane	As above

Furthermore, while neutrophil counts return to normal after each cycle of chemotherapy, recovery of lymphocytes is much slower. Recovery of B lymphocytes has been observed to occur during maintenance chemotherapy, but T lymphocyte counts, particularly CD4+ T cells, remain low for over 6 months after chemotherapy.[6-8] Lymphocyte proliferation responses to mitogens and specific antigens may remain abnormal for 12 months or longer post-chemotherapy.[8, 9] Various risk factors for delayed immune reconstitution have been reported, including younger age, older age, and high-risk ALL.[6-8] Children with delayed recovery of adaptive immune function may remain at increased risk of invasive infections long after they have returned to school and other community activities where their risk of exposure is high.

## 1.2 Vaccine-preventable infections and waning vaccine-induced immunity

ALL disproportionately affects children under 5 years of age, most of whom have not completed their preschool immunizations at the time of diagnosis.[1] These children are at high risk of complications from vaccine-preventable infections such as measles, varicella-zoster, and *Streptococcus pneumoniae*.[10-13] Measles can be particularly severe in children with cancer, with 80% of patients suffering complications such as pneumonitis, and mortality of up to 70%. [12] Children with ALL who are non-immune to varicella are at high risk of disseminated disease leading to pneumonitis and hepatitis.[10] Among children and adults with leukemia, the risk of invasive pneumococcal disease (IPD) has been reported to be 10 to 12-fold higher than in the general population.[13, 14] Additionally, vaccine failures leading to invasive infections, such as *Haemophilus influenzae* type b (Hib), have been reported in fully immunized children with ALL who were later found to have decreased titres to multiple vaccines.[15, 16] Herd protection may mitigate the risk of vaccine-preventable infection associated with waning vaccine immunity. There has been a recent resurgence of vaccine-preventable infections, such as measles and pertussis related to decreased vaccine coverage and/or inadequate duration of vaccine-induced protection among healthy children.[17, 18] While overall vaccine coverage rates in Canada have been stable over the past decade, coverage for several vaccines is below the 90-95% level needed for reliable herd protection.[19, 20] Additionally, vaccine coverage is not uniform; areas with

large numbers of underimmunized children can be more susceptible to disease outbreaks.[21] Outbreaks have also occurred in communities with high vaccine coverage, for example in Quebec in 2011 where over 700 cases of measles occurred in a community with >90% measles vaccine coverage.[22] Children with ALL typically return to school and community activities while they are on maintenance therapy, which puts them at risk of exposure to infectious diseases. The failure of herd protection in these cases underscores the importance of ensuring optimal immunization of children with ALL.

There is increasing evidence that antibody titres to vaccine antigens decrease over time in children who were fully vaccinated prior to chemotherapy.[23-26] A systematic review found that 25-35% of patients who had completed chemotherapy had antibody levels to tetanus and diphtheria that were below protective levels and 70% were susceptible to pertussis.[26] Among 80 children with ALL treated between 2001 and 2010, approximately 30% of those who were seropositive to measles and 17% who were seropositive for varicella at diagnosis subsequently lost immunity to those antigens.[25] In another study of 100 ALL patients who were a mean of 2 years post-chemotherapy, only 42-86% had protective titres to routine childhood vaccines including Hib, hepatitis B, diphtheria and rubella, compared to 96-100% of healthy controls.[23] Seventy-three percent of subjects had non-protective titres to  $\geq 2$  antigens. Studies conducted prior to the introduction of universal infant pneumococcal conjugate vaccination (PCV) reported that pneumococcal antibody concentrations were significantly lower in children with ALL who were 3-6 months post-chemotherapy compared to age-matched healthy controls.[27, 28] No published studies have evaluated the impact of infant PCV immunization on pneumococcal titres post-chemotherapy.

### **1.3 Vaccination post-chemotherapy**

Responses to booster immunizations given after chemotherapy are variable, with poorer responses observed in children with high-risk versus standard-risk ALL in some studies.[24, 26, 29] In one study of 46 children with ALL ages 1 to 18 years who were  $\geq 6$  months post-chemotherapy, immunization with one dose of combined diphtheria-tetanus-pertussis-polio-Hib vaccine (DTaP-IPV-Hib), followed one month later by measles-mumps-rubella (MMR) and meningococcal serogroup C conjugate vaccine (MenC-C) resulted in significant increases in antibody titres with over 90% of subjects achieving protective levels and/or achieving a  $\geq 4$ -fold increase in titres.[29] At one year post-immunization there was evidence of long-term protection against tetanus and measles in all patients tested. Other studies similarly reported good short-term responses to DT, Hib and MMR vaccination, but long-term responses were not measured.[24, 30] No published studies have assessed the impact of PCV13 booster immunization on pneumococcal titres, but one study of 10-valent pneumococcal conjugate vaccine (PCV10) administered to children with ALL on chemotherapy found that 60% achieved titres  $>0.35$   $\mu$ g/ml (WHO standard for protection [31]) to 7/10 PCV serotypes.[32] These studies must rely on assessment of serologic correlates of protection because vaccine efficacy cannot be evaluated due to the low incidence of most vaccine-preventable infections in this small patient population.

Guidelines in the United Kingdom and Australia recommend booster doses of routine vaccines such as DTaP, IPV, Hib, MMR and MenC-C for all patients with leukemia starting 6 months

after chemotherapy, but compliance with guidelines appears to be suboptimal.[33-35] The Australian guidelines also recommend administering one dose of PCV13 at least 6 months after completion of chemotherapy in patients not previously immunized followed by 23-valent pneumococcal polysaccharide vaccine (PPV23). However, a recent guideline by the Infectious Disease Society of America (IDSA) made no recommendations regarding booster vaccinations, citing insufficient evidence of the benefit of such an approach.[4]

In Canada, there is no standard of care for immunization of children after chemotherapy for ALL. The National Advisory Committee on Immunization (NACI) recommends one dose of PCV13 followed by PPV23 in patients at high risk of IPD, including those with malignancies.[36]

#### 1.3.1 Immunization Practices in Canada

To better understand immunization practices for patients with ALL at Canadian pediatric oncology centres, we conducted a survey of the 16 centres in the C group of pediatric oncology and bone marrow transplant centres in Canada. The survey was launched in October 2014. The results revealed wide variability in practices among the 10 centres responded. Four centres routinely provide immunizations after chemotherapy and at a fifth centre antibody titres are routinely measured and booster doses are recommended for patients with low titres. At one centre, the respondent remarked that his/her personal practice was to routinely measure titres and offer booster vaccinations but his/her colleagues' practices varied. Four centres administer PCV13 and one administers PPV23 to children who have completed chemotherapy. Centres initiate immunization with inactivated vaccines either 3 or 6 months post-chemotherapy (at 4 and 6 centres, respectively), while live-attenuated vaccines are administered 3, 6 or 12 months post-chemotherapy across the ten participating centres. Respondents at only two centres reported that AEFI are monitored in patients with ALL, while three respondents were unsure.

### **1.4 Vaccine safety**

Studies of vaccine safety in immunocompromised patients have primarily focused on live attenuated vaccines (e.g., MMR, varicella).[4, 37, 38] One study demonstrated a similar risk of herpes zoster after varicella immunization, compared to natural infection, in children with ALL on maintenance chemotherapy.[38] There is one report of death in a child with ALL after varicella immunization, although that child was receiving chemotherapy.[39] One study of 39 children immunized with PCV10 while on chemotherapy for ALL reported local reactions in 73% and systemic symptoms in 41%, most frequently diarrhea. Only one patient experienced fever.[32] The systemic symptoms were considered to be most likely chemotherapy-related. The risk of adverse events following immunization (AEFI) with inactivated vaccines is assumed to be similar in immunocompromised children compared to healthy children, but the data supporting this assumption are limited.[4] Further data on the frequency, severity and impact of AEFI in children with ALL are needed.

### **1.5 Rationale**

NACI has identified vaccine safety and effectiveness in immunocompromised individuals as a research priority for vaccines recently introduced in Canada (e.g., PCV13).[36] Among

physicians caring for pediatric ALL patients, there is currently a lack of empirical scientific evidence to guide immunization practices, which has likely contributed to the variation in practices observed in our survey. Although universal PCV immunization programs have been in place for a decade or more in many developed countries, there is a paucity of literature evaluating these vaccines in children with ALL. Infants have been immunized routinely with PCV in Canada since at least 2006, and the 13-valent vaccine has been available since 2010. Most children completing chemotherapy for ALL would have been immunized in infancy with PCV7, but many would never have received a dose of PCV13 or PPV23, which is not routinely administered to healthy children. Due to waning humoral immune responses, children who received PCV13 prior to diagnosis with ALL may also benefit from an additional dose of PCV13, and from PPV23 immunization. It is unclear whether children with ALL are receiving all recommended immunizations and whether they would benefit from additional booster doses of other vaccines such as tetanus-diphtheria-pertussis-containing vaccines (i.e., DTaP) after they complete chemotherapy.

This study will be the first multi-centre study of vaccination in ALL survivors in Canada and among the largest prospective vaccination studies to date in this population. It will provide critical information to identify children with ALL who may be at greater risk for vaccine-preventable infections due to low antibody titres, and will assess immunogenicity and safety of PCV13 and DTaP-IPV-Hib in this population. The study results will support the development of immunization recommendations for children with ALL. This study will also test a methodology to assess vaccine immunogenicity and safety in a high-risk population that, if successful, will be expanded to other groups of immunocompromised children and adults, such as patients who received bone marrow transplants, have primary immunodeficiency or are on high dose steroids.

This study will be led by the Special Immunization Clinic (SIC) network as part of the Public Health Agency of Canada/Canadian Institutes for Health Research (PHAC/CIHR)-funded Canadian Immunization Research Network (CIRN), in collaboration with pediatric oncologists at the study sites. The SIC network, originally part of the PHAC/CIHR Influenza Research Network (PCIRN), was established in 2013 at 13 tertiary care centres across Canada to provide expertise in the clinical care of patients with prior AEFI and potential contraindications to immunization. SIC investigators employ a standard approach to patient assessment, vaccination and follow-up. De-nominalized data are transferred to a central database with patient consent. The network was designed as both a clinical service and a platform for research studies. Thus, the SIC Network is uniquely positioned to lead this study.

## **2. Objectives**

- To identify risk factors for low baseline antibody titres to pneumococcal serotypes, tetanus, pertussis toxin, and varicella in previously immunized children diagnosed with ALL at  $\geq 1$  year of age who completed chemotherapy within 6-12 months, as compared to immunocompetent age-matched controls.
- To assess short and long-term immune responses to PCV13 followed by PPV23 in children immunized 6-12 months after completing chemotherapy for ALL.

- To assess short and long-term immune responses to a DTaP-IPV-Hib booster in children immunized 6-12 months after completing chemotherapy for ALL.
- To estimate the frequency of medically-attended AEFI in children immunized after completing treatment for ALL.

### 3. Methods

#### 3.1 Study design

This will be a prospective multi-centre open-label clinical trial at 10 pediatric centres that are members of the SIC network and the C council which is comprised of the heads of the 16 pediatric oncology and blood and marrow transplantation programs in Canada. Each participating site is run by a Site Investigator in conjunction with a nurse coordinator (SIC nurse). The coordinating site will be the Canadian Center for Vaccinology at the IWK Health Centre, Halifax, NS.

Children who were diagnosed with ALL at  $\geq 1$  year of age, are within 3-12 months of completing chemotherapy, and have not received immunizations other than influenza since completing chemotherapy will be eligible. As most centres initiate immunization at 6 months post-chemotherapy, children will be enrolled and immunized at the 6-month visit, where possible. Children can be enrolled as late as 12 months post-chemotherapy if they meet all other eligibility criteria. All participants will undergo a clinical assessment, and immunologic and serologic testing for pneumococcus, tetanus, pertussis and varicella. They will then be immunized with PCV13, DTaP-IPV-Hib, regardless of immunization history [unless PPV23 was received within the prior 12 months (see section 3.2.1)]. Other routine vaccines required as per provincial and centre-specific immunization policies will also be administered. Pneumococcal polysaccharide vaccine (PPV23) will be administered approximately 2 months after PCV13. Repeat serologic testing will be conducted at 2-3 months and 12-15 months after DTaP-IPV-Hib and PCV13 immunization to assess short and long-term immune responses.

Study visits and bloodwork will be coordinated with routine blood draws wherever possible. Baseline antibody titres will be compared to age-matched immunocompetent controls. Vaccine responses will be compared to healthy vaccine recipients in published clinical trials. Multivariable analysis will be conducted to identify predictors of low baseline antibody titres after chemotherapy and poor immune responses to vaccination.

Adverse events following immunization will be captured through standardized telephone interviews conducted by the SIC nurse coordinator on days 8-10 and 30-33 post-immunization. Severity of AEFI will be classified as outlined in section 5.3 and a formal causality assessment based on a published algorithm (e.g., [40]) will be conducted for all events of moderate impact or greater (see section 5.3.1 for definitions).

## 3.2 Subjects, recruitment and consent

### 3.2.1 Cases

#### *Inclusion criteria*

- Diagnosed with standard risk, high risk or very high risk ALL
- Age at diagnosis:  $\geq 1$  year of age (age at enrollment:  $\geq 3$  years)
- Completed chemotherapy 3 to 12 months prior to enrollment
- No evidence of ALL relapse or secondary malignancy
- No known primary immunodeficiency
- No receipt of pneumococcal or tetanus-containing vaccines since completing chemotherapy
- No history of allergy to any component of PCV13
- Caregiver and/or participant is English or French-speaking and able to provide written informed consent

#### *Exclusion criteria*

- Infantile ALL
- Evidence of disease relapse or secondary malignancy
- History of underlying primary immunodeficiency
- Transplant recipient
- Received intravenous immunoglobulin (IVIG) within past 9 months or other blood products within the prior 3 months.
- Children who received PPV23 within 12 months of enrollment will not be eligible to receive PCV13 or PPV23. These children can still participate in the baseline evaluation, receive DTaP-Hib-IPV vaccine, and have tetanus and pertussis serology measured at 2 and 12-15 months post-immunization.

### 3.2.2 Controls:

#### *Inclusion criteria*

- Children 3-18 years of age, age-matched to cases
- Caregiver and/or participant is English or French-speaking and able to provide written informed consent

#### *Exclusion criteria*

- History of primary or secondary immunodeficiency including aplastic anemia, malignancy, nephrotic syndrome, malabsorption or severe malnutrition
- Immunosuppressive therapy within 3 months of enrollment (excluding inhaled corticosteroids)
- Received intravenous immunoglobulin (IVIG) within past 9 months or other blood products within the prior 3 months.

### 3.2.3 Recruitment and Consent

The oncologists and/or clinic nurses will identify potentially eligible subjects with ALL.

Caregivers of eligible patients will then be approached to participate in the study during routine outpatient visits to the pediatric oncology clinic. The consent form will be reviewed with caregivers by a research nurse, oncologist or oncology clinic nurse. Participants' and caregivers' questions will be answered and written informed consent will be obtained.

Children 3-18 years of age who are not immunocompromised will be recruited as controls from among children requiring venous blood draws in the outpatient laboratory, siblings of participants with ALL, prior study participants who have consented to future contact, and other methods depending on the study site. Caregivers of potentially eligible children will be approached by study staff in the outpatient laboratory or clinic, or contacted by the study team via telephone, email or mail and invited to participate. As above, written informed consent will be obtained after the consent form is reviewed and the participants' and caregivers' questions have been answered. Controls will be frequency age-matched to cases to ensure that the age distribution of cases and controls is similar. Three participating sites will be responsible for recruiting approximately 75 control subjects. The coordinating site will conduct the age-matching of controls to cases.

## 4. Study Plan

### 4.1 Timeline

July–December 2014: Protocol development (pending final results of an institutional survey of immunization practices at pediatric oncology and HSCT centres)  
January 2015–April 2015: External scientific review, finalize protocol  
May – June 2015: Finalize REB documents, REB submission  
November 2015–August 2017: Patient recruitment/enrollment (22 months)  
April 2017–January 2018: Recruitment of control subjects  
August 2018: Patient follow-up completed  
December 2017–January 2019: Laboratory analysis; data analysis, presentation of preliminary results, manuscript preparation  
January–March 2019: Final data analysis  
March–May 2019: Complete final manuscripts, presentations

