### **6.3 Variables**

#### **6.3.1 Outcomes**

The primary outcomes are the proportion of participants with protective titres ( $\geq 0.35 \mu\text{g/ml}$ ) to the PCV13 serotypes tested, at baseline (compared to age-matched controls), 2 months and 12-15 months post PCV13+PPV23.

Secondary outcomes include baseline GMTs and frequency of protective titres to varicella, pertussis toxin and tetanus among ALL patients versus controls, short-term (baseline to 2 months after vaccination) and long-term (baseline to 12-15 months) vaccine responses to DTaP, based on GMT ratios, the proportion of subjects with protective titres (e.g., tetanus, varicella) and/or the

proportion with an adequate immune response (defined as GMT ratio  $\geq 4$  at 2 and 12-15 months post-vaccination).

**Safety assessment:** The primary outcome is frequency of AEFI of moderate impact or greater (see definitions in section 5.3). The secondary outcomes are frequency of any AEFI and frequency of AEFI deemed to be causally associated with vaccination.

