## **6.4 Statistical Methods**

**Immune responses:** Immune markers (see 5.2) will be compared to age-specific reference values. Baseline GMTs with 95% confidence intervals and proportion with protective titres at baseline will be reported for cases and controls, stratified by interval since last vaccination. Varicella titers will be compared pre-chemotherapy (i.e., at diagnosis) and post-chemotherapy and the proportion with loss of immunity will be reported. The proportion of subjects with GMT ratios  $\geq 4$  or protective titres at 2 and 12-15 months post-vaccination will be reported for pneumococcal vaccines (PCV13+PPV23) and DTaP-IPV-Hib, stratified by age, ALL treatment protocol (COG versus DFCI), interval from last chemotherapy to immunization, and ALL risk category. Vaccine responses will be compared to the expected responses in healthy children based on published clinical trials. Differences among categorical variables will be assessed by Pearson's  $\chi^2$  test or with Fisher exact test when expected cell sizes are  $< 5$ . Independent predictors of low baseline GMTs to tetanus toxoid and pneumococcal serotypes and of an adequate immune response to PCV13+PPV23 vaccination and DTaP-IPV-Hib booster will be assessed using multivariable regression models.

**Safety assessment:** The frequency of low impact, moderate impact and high impact or serious AEFI will be reported by vaccine type, age and ALL risk category, and compared to the published frequencies in healthy children. The frequency of events deemed to be related to vaccination based on the causality algorithm will also be reported.

All statistical analyses will be conducted using SAS® version 9.4 (Cary, NC).

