### **7.1 Potential Harms and Benefits**

Clinical assessments will be performed as per routine clinical care. Blood samples for this study will be collected in conjunction with routine blood draws for clinical care when possible and the minimum additional volume required to conduct the required tests will be collected (5 to 15 ml). There is the risk of discomfort related to venipuncture in some patients with ALL who would only require blood by fingerstick for their routine tests (e.g., CBC).

Participants with ALL may experience adverse events following PCV13, PPV23 or DTaP-IPV-Hib immunization. For most participants, administration of these vaccines will be consistent with NACI guidelines. Expected adverse events include local reactions, fever, headache, and malaise. In patients who have previously received a full infant series of PCV13 (2, 4 and 12 months) prior to chemotherapy, they may be at higher risk of developing a large local reaction at the injection site (pain, swelling, erythema  $\geq 10$  cm diameter). Such reactions can be managed with acetaminophen or non-steroidal anti-inflammatory agents. There is also a risk of large local reactions after DTaP-IPV-Hib in children  $\geq 7$  years of age. As discussed in section 4.6, the vaccine schedule proposed in this study is in keeping with current practice at some Canadian centres and in other jurisdictions. There is a small risk of unexpected adverse events. Participants will be monitored for adverse events as outlined above.

There will be direct benefits to participants with ALL. They may receive a more detailed clinical and immunological assessment than would be routinely conducted, and will receive close follow up after vaccination. In some cases they will receive additional vaccines that may not be routinely administered at all sites and which are expected to confer additional protection against

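### Age-matched controls are recruited about 11 months later than cases, so for the serotypes PCV13 added, the baseline comparison partly reflects infant vaccine product

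*Combined protocol and SAP*

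**What the plan says.** Section 4.1 gives two recruitment windows: "November 2015–August 2017: Patient recruitment/enrollment (22 months" and "April 2017–January 2018: Recruitment of control subjects". Section 3.2.3 sets the matching: "Controls will be frequency age-matched to cases to ensure that the age distribution of cases and controls is similar". It names no other matching factor, band width or reference date for age.

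Section 1.5 describes the vaccine background: "Infants have been immunized routinely with PCV in Canada since at least 2006, and the 13-valent vaccine has been available since 2010". It adds: "Most children completing chemotherapy for ALL would have been immunized in infancy with PCV7, but many would never have received a dose of PCV13".

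Section 6.3.1 begins "The primary outcomes are the proportion of participants with protective titres" and sets the threshold at 0.35 µg/ml for the PCV13 serotypes tested. The baseline part of that outcome is compared with the age-matched controls.

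Section 6.4 reports baseline results for cases and controls "stratified by interval since last vaccination". It names unadjusted tests for categorical variables (Pearson χ² or Fisher). It also plans multivariable models for predictors of low baseline GMTs but does not name their covariates. Vaccine products received is among the independent variables in 6.3.2. It is not assigned to the case-control comparison.

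**The concern.** Two children of the same age sampled at different calendar times have different birth dates. Here the later-sampled group is the controls, and the relevant birth years straddle the change from PCV7 to PCV13. A control is therefore somewhat more likely than a case of the same age to have had PCV13 in infancy. For a serotype that PCV13 added, part of any case-control difference could then come from the infant vaccine rather than from leukemia and its treatment.

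The comparison is a primary outcome, and a lower proportion protected among cases would be read as loss of immunity after chemotherapy. The distortion is systematic, so recruiting more children would not remove it.

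**Working it through.** **1. Calendar gap.** November 2015 to August 2017 is 22 months, which reproduces the stated figure. April 2017 to January 2018 is 10 months. With even accrual the midpoints are 1 November 2015 + 11 months = 1 October 2016 and 1 April 2017 + 5 months = 1 September 2017, a gap of 11.0 months. The windows share April to August 2017 (5 months). If mean accrual falls one third or two thirds of the way through each window, the gap runs from 5.7 to 16.4 months.

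**2. Age mix.** Section 1.1 gives incidences of 9 per 100,000 at ages 1 to 4 and about 5 per 100,000 overall. With equal population at each age from 0 to 14, the share diagnosed at 1 to 4 is 4 × 9 / (15 × 5) = 48%. The remaining 52% are spread evenly over ages 5 to 15 (assumption). Age at Visit 1 adds 2 or 3 years of treatment (1.1.1, equal sex split assumed) and 6 to 12 months after chemotherapy (section 2). Controls are given the same age distribution.

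**3. Share born after the switch.** The documents date the switch only to 2010. Infant doses fall at 2, 4 and 12 months (7.1), so a first PCV13 dose is possible for births up to about a year earlier. Several birth cut-offs were therefore simulated, with even accrual:

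| Born on or after | Cases | Controls | Gap (points) |
|---|---|---|---|
| January 2009 | 41.2% | 49.6% | 8.4 |
| July 2009 | 35.8% | 45.6% | 9.7 |
| January 2010 | 30.0% | 40.7% | 10.7 |
| July 2010 | 24.0% | 35.0% | 10.9 |
| January 2011 | 18.0% | 29.0% | 11.0 |

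Gaps were taken before rounding. As a hand check of the upper value, the younger group's ages at diagnosis spread over 4 years, so the gap is about 0.48 × (1/4) × (11/12) = 0.11. If ages are instead even from 3 to just under 19, it is (11/12)/16 = 0.057, about 6 points.

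**4. Bias.** Bias = gap × effect of product on the proportion protected. The documents give no product effect, so 10 to 60 points is assumed.

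- Gap of 10 points: 0.10 × 0.10 = 1 point, up to 0.10 × 0.60 = 6 points.
- Gap of 6 points: 0.6 to 3.6 points.

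The target difference in 6.2 is 20 points. With 75 per group and 60% protected, the standard error is √(2 × 0.6 × 0.4 / 75) = 0.08. A bias of 1 to 6 points raises the two-sided 5% error rate to about 5.2% to 11.7%.

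**5. Serotypes exposed.** Section 5.2 lists 14 serotypes, of which 3 are only in PPV23. The other 11 are taken as PCV13 serotypes. A 7-valent vaccine covers at most 7 of them, so at least 11 − 7 = 4 were added by PCV13.

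**6. Whether the planned stratification removes it.** Take a seven-year-old case sampled in November 2015: born November 2008, last infant dose November 2009, before PCV13 was available. Take a seven-year-old control sampled in January 2018: born January 2011, first dose March 2011, after it became available. Both are six years from their last infant dose. They match on age and on interval but can differ in product. These are the extremes of the windows, chosen to show that interval does not identify product.

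**The case against.** The strongest reply is that the effect is small and the plan already holds the means to handle it. Records are obtained for both groups, product is a listed variable, and models for low baseline pneumococcal GMTs are planned. This partly stands: the data exist and only wording is missing. But those models have no named covariates, and nothing says that the case-control difference in proportions protected is adjusted.

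Birth date is also an imperfect proxy for product. Section 1.3 reports a national recommendation for PCV13 in patients with malignancies, and 6.3.2 records doses given during chemotherapy. Some earlier-born cases may therefore have had PCV13, which would narrow the gap. This stands, and it is why recorded PCV history is a better adjuster than birth year.

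Three stronger readings are tempting and not supported:

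- **Controls as a group lie on the other side of the switch from cases.** The windows overlap, and only about 1 in 10 controls changes cohort.
- **All cases are young, say 3.5 to 7.5 years, which would roughly double the gap.** That would put 56% to 81% of cases after the switch, against the expectation in 1.5 that most had PCV7. A boy diagnosed just before age 5 would also be about 8.5 to 9 at Visit 1.
- **The whole primary outcome is affected.** Up to 7 of the 11 serotypes may be common to both vaccines, and the post-vaccination parts of the outcome do not use these controls.

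Section 4.2 makes control serology depend on the vaccines received, without saying how this affects the serotypes tested. This point does not rest on that clause.

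**Conclusion.** The concern holds at modest size. Staggered recruitment with matching on age alone places about 8 to 11 points more controls than cases in PCV13-era birth cohorts (about 6 with ages spread evenly). For the added serotypes, this probably overstates the deficit in cases by about 1 to 6 points against a 20-point target, and the stated stratification does not remove it.

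The mechanism and the missing product adjustment come directly from the documents. The size rests on assumptions: even accrual, matching on age at enrolment, the age mix above, the month of the switch, and above all the product effect. The cohort gap moves roughly in proportion to the calendar gap, so uneven accrual could make it about half (5.7/11.0) to one and a half times (16.4/11.0) as large. The direction assumes that PCV13 recipients are more often protected against the added serotypes.

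**What to change.** In 6.4, state that the baseline case-control pneumococcal comparison is stratified by, or adjusted for, PCV history before sampling: any PCV13 dose versus PCV7 only. Say where children with no recorded PCV dose are placed. Report the serotypes PCV13 added separately from the PCV7 serotypes, and show birth-year distributions for cases and controls.

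Keep number of doses for a sensitivity analysis. ALL can interrupt the schedule, so adjusting for doses in the main analysis could remove part of the effect being studied.

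Matching controls on birth year is not advised. In the present windows it would make them about 11 months older than cases at sampling and undo the age match.

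The cost is a few lines of analysis text and slightly wider intervals. Immunization records and month and year of birth are already collected.
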